**Table 4. Part 2 Schedule of Assessments**

Visit Number	Visit 1	Visit 2	Visit 3	Visit 4	Visit 5	Visit 6	Visit 7	Visit 8	Visit 9	Visit 10	Visit 11	Visit 12	Visit 13	Visit 14
Study Day/Week	Screening	Day 1	Week 1 (telephone)	Week 2	Week 4	Week 8 (telephone)	Week 12	Week 18	Week 24	Week 30 (telephone)	Week 36	Week 42 (telephone)	Week 48 End of Treatment	Week 52 a End of Study/ 4-week follow-up
Day Relative to First Dose	-60 to -1 b	1 c	7 (±3 days)	14 (±3 days)	28 (±3 days)	56 (±3 days)	84 (±3 days)	126 (±3 days)	168 (±3 days)	210 (±3 days)	252 (±3 days)	294 (±3 days)	336 (±3 days)	364 (±3 days)
Informed consent	X													
Inclusion/Exclusion criteria assessment	X	X												
Demographics and baseline disease characteristics	X													
Pes cavus assessment	X													
Foot X-ray	X d													
Prior and concomitant medication assessment	X	X	X	X	X	X	X	X	X	X	X	X	X	X
Medical history	X													
Height	X													
Echocardiogram	X e								X				X	
Electrocardiogram	X e			X	X		X	X	X		X		X	X
Vital sign measurements	X	X		X	X		X	X	X		X		X	X
Weight and BMI	X	X		X	X		X	X	X		X		X	X
Physical examination	X								X				X	X
Adverse event collection		X	X	X	X	X	X	X	X	X	X	X	X	X
Clinical chemistry	X f	X		X	X		X	X	X		X		X	X
Hematology	X f	X		X	X		X	X	X		X		X	X
Urinalysis and microscopy	X f	X		X	X		X	X	X		X		X	X
BNP and NT-proBNP g	X f	X		X	X		X	X	X		X		X	X
Hepatitis B and C and HIV h	X th													
Pregnancy test WOCBP i	X ti	X		X	X		X	X	X		X		X	X
Exercise regimen reporting	X	X												
Randomization		X												
Study drug dispensation		X			X		X		X		X			
Study drug return and pill count / diary j					X		X		X		X		X	
Study drug administration k			←-----X-----→											

Visit Number	Visit 1	Visit 2	Visit 3	Visit 4	Visit 5	Visit 6	Visit 7	Visit 8	Visit 9	Visit 10	Visit 11	Visit 12	Visit 13	Visit 14
Study Day/Week	Screening	Day 1	Week 1 (telephone)	Week 2	Week 4	Week 8 (telephone)	Week 12	Week 18	Week 24	Week 30 (telephone)	Week 36	Week 42 (telephone)	Week 48 End of Treatment	Week 52* End of Study/ 4-week follow-up
Day Relative to First Dose	-60 to -1 b	1 c	7 (±3 days)	14 (±3 days)	28 (±3 days)	56 (±3 days)	84 (±3 days)	126 (±3 days)	168 (±3 days)	210 (±3 days)	252 (±3 days)	294 (±3 days)	336 (±3 days)	364 (±3 days)
Maximal exercise test d	X	X			X		X	X	X		X		X	
Neurologic FARS (practice)	X m													
Neurologic FARS n	X o	X o			X		X	X	X		X		X	
9-hole peg test	X	X							X				X	
25-foot timed walk test	X	X p							X p				X p	
Video Collection of Normal Walking q		X							X				X	
SF-36 Health Survey Update		X							X				X	
Activities of Daily Living	X								X		X		X	
Patient Global Impression of Change							X r		X r		X r		X r	
Clinical Global Impression of Change							X r		X r		X r		X r	
Falls Diary	X s		←-----X-----→											
PK analysis				X t			X u		X u				X u	

Abbreviations: BMI=body mass index; BNP= B-type natriuretic peptide; FARS=Friedreich’s ataxia rating scale; HIV=human immunodeficiency virus; NT-proBNP=N-terminal prohormone of B-type natriuretic peptide; PK=pharmacokinetic; WOCBP=women of childbearing potential.

a These procedures should also be performed in the event of early termination.

b Study Day -1 is the day prior to first dose of study drug.

c All Day 1 procedures should be performed prior to administration of first dose of study drug.

d Only 1 x-ray will be collected during the study. Only x-rays of the right foot will be completed for the foot x-ray assessment. Patients should complete the x-ray foot assessment at Screening; however, if the patient was not able to complete the x-ray foot assessment at Screening, it may be completed during any visit while the patient is participating in the study.

e For patients with echocardiograms and electrocardiograms collected within 90 days prior to the Screening Visit, the most recent echocardiogram and electrocardiogram can be used to assess patient eligibility.

f A home health nurse visit may be used to collect all lab samples required at the Screening Visit.

g Patients must be allowed to rest for a minimum period of 1 hour following maximal exercise test before this blood sample is collected (at the same time as all central lab blood draws). This sample should be taken with the patient in the same position (e.g., sitting or semi-recumbent) at all appropriate visits.

h Blood samples should be collected for hepatitis B and C and HIV antibodies only in patients lacking evidence of a negative titer in the past year.

i Negative serum pregnancy test results are required at the Screening Visit before study enrollment, and negative urine pregnancy test results are required at all other times indicated for continued participation in the study.

j A dosing diary check must be performed at study drug return and pill count.

- k Study drug should be administered in the presence of study staff in the clinic on Day 1 after all Day 1 assessments have been completed. Study drug should also be administered in the clinic on Day 14 (Visit 4), Day 84 (Visit 7), Day 168 (Visit 9), and Day 336 (Visit 13) after the blood collection for predose PK analysis. All other doses can be administered at home. Study drug should be administered once daily through Day 336 (Visit 13).
- l On study days where multiple assessments are to be completed, the maximal exercise test will be the first functional assessment performed.
- m The practice FARS assessment is not required for patients having completed a FARS assessment within 90 days prior to Screening. The practice FARS assessment must be performed prior to the screening maximal exercise test.
- n Other than the practice FARS, all FARS assessments must always be performed after the maximal exercise test.
- o Both Screening and Day 1 mFARS are required to determine patient eligibility.
- p Video of the 25-foot timed walk test is optional and will be collected only for those patients who provide consent to video.
- q Patients who consent to video collection of the 25-foot timed walk test will also have video collection during normal walking with a 25-foot (un-timed) walk using his/her normal gait. The normal walk must be performed after the 25-foot timed walk test.
- r Patients and investigators must complete the patient global impression of change and clinical global impression of change following completion of the neurological FARS exam.
- s Patients will be provided the fall diary at Screening and must record fall incidents between Screening and Week 48.
- t Blood samples for PK analysis at Day 14 (Visit 4) should be collected prior to study drug administration as well as 1, 2, 4, and 8 hours after study drug administration.
- u A single blood sample for PK analysis at Day 84 (Visit 7), Day 168 (Visit 9), and Day 336 (Visit 13) should be collected prior to study drug administration.

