#### **9.9.10. Electrocardiogram**

A 12-lead electrocardiogram (ECG) will be recorded at the times indicated in [Table 3](#) and [Table 4](#) after the patient has rested for approximately 10 minutes in a supine position. The heart rate from the ECG machine should not be used as part of the vital sign measurements.

An ECG is required for eligibility. If a patient has had an ECG completed within 90 days prior to the Screening Visit, the most recent ECG can be used as the screening assessment for patient eligibility.

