**11.2.8. Activities of Daily Living**

The change in ADL from Baseline at Weeks 24, 36, and 48 will be analyzed.

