## **12. SAFETY ASSESSMENTS**

### **12.1. Safety Parameters**

Safety parameters in Part 1 and Part 2 include results of echocardiogram, ECG, vital sign measurements, weight, BMI, physical examination, AEs, SAEs, concomitant medications, and laboratory tests (clinical chemistry, hematology, urinalysis, microscopy, assessment of BNP and NT-proBNP, and pregnancy tests [as indicated]). Safety parameters in the extension study include vital sign measurements, physical examination results, AEs, SAEs, weight, and laboratory tests (clinical chemistry, hematology, urinalysis, microscopy, assessment of BNP and NT-proBNP, and pregnancy tests [as indicated]).

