**Week 48 Visit: Maximal Exercise Test**  
*Source Document*

Visit Date (dd/MMM/yyyy): ____/____/____	
Was Maximal Exercise Test performed?	 Yes  No
If no, specify reason:  Not Applicable	
Height:	_____ in. OR _____ cm
Weight:	_____ pounds OR _____ kilograms
Resting Data (record measurements while subject is at rest in supine position)	
Start Time:	_____ : _____
Was resting ECG collected?	 Yes → Print ECG data for source  No → Specify: _____
Heart Rate	_____ beats/min
Oxygen saturation by pulse oximeter (SpO2)	_____ %
Resting Blood Pressure	Systolic Reading : _____ mm Hg
	Diastolic Reading: _____ mm Hg
Resting minute oxygen consumption (VO2)	_____ L/min
Resting Pulmonary Function Performed via Spirometry (Please capture data by hand if it is not captured electronically by metabolic cart)	
Forced Vital Capacity (FVC)	_____ L
Forced expiration volume with one second (FEV)	_____ L
Maximum voluntary ventilation (MVV)	_____ L/min
Predicted Forced Vital Capacity	_____ %
Warm-up	
Warm-up Start Time:	_____ : _____
Was patient able to maintain 65-75 rpm at no resistance?	 Yes  No
BORG in warm-up	_____

Site ID: \_\_\_\_\_ Patient ID: \_\_\_\_\_ Patient Initials: \_\_\_\_\_

Protocol 408-C-1402-Part 2

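### Part 2 schedules neither ADL nor the safety ECG on Day 1, so the ADL baseline can be up to 60 days old and the last pre-treatment ECG in the schedule, at worst, 150 days old: a minor loss of precision, not bias between arms

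*Protocol*

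**What the plan says.** Table 4 of the protocol (Section 7.7) marks the Part 2 ECG at Screening and at Weeks 2, 4, 12, 18, 24, 36, 48 and 52. It marks ADL at Screening and at Weeks 24, 36 and 48. The Day 1 cell is empty in both rows.

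The screening window runs from Day -60 to Day -1, and footnote b fixes the count: "Study Day -1 is the day prior to first dose of study drug". Footnote e, attached to the Screening ECG, accepts older recordings: where a patient has earlier "electrocardiograms collected within 90 days prior to the Screening Visit, the most recent echocardiogram and electrocardiogram can be used to assess patient eligibility". Section 9.9.10 repeats the allowance, saying that "the most recent ECG can be used as the screening assessment for patient eligibility".

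For the endpoints, Section 11.2.8 states: "The change in ADL from Baseline at Weeks 24, 36, and 48 will be analyzed". Section 12.1 states: "Safety parameters in Part 1 and Part 2 include results of echocardiogram, ECG, vital sign measurements". Safety and tolerability is a Part 2 primary objective (Section 6.2.1); ADL is exploratory (Section 6.2.3).

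Day 1 is an existing clinic visit at which all procedures precede the first dose (footnote c). It already carries vital signs, weight, laboratory tests, BNP, the maximal exercise test, FARS, the 9-hole peg test, the timed walk and SF-36.

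**The concern.** Most Part 2 measurements are taken or repeated immediately before dosing. ADL and the safety ECG are not, and no reason is given. The protocol's other schedules show that Day 1 is workable: Part 1 (Table 3) marks an ECG on Day 1, and the Extension (Table 5) marks ADL on Day 1.

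For ADL, whatever change occurs between Screening and first dose is counted as change on treatment, over a lead that differs from patient to patient.

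For ECG, the stake is attribution in the individual patient. Section 12.6 treats conditions present before the first dose as medical history, while Section 12.2.1.1 treats new or worsened findings after it as adverse events. If the Week 2 ECG is abnormal and the last scheduled tracing is months old, the ECG schedule alone does not show on which side of the first dose the change arose. The population may include patients with mild to moderate cardiomyopathy (Section 8.2), so the question is a realistic one.

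**Working it through.** The plan states no maximum baseline age, so there is no figure to reproduce. The check is schedule arithmetic.

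**Inputs**
- Earliest Screening: Day -60 (Table 4). Day -1 is one day before first dose, so Day -60 is 60 days before it.
- ECG look-back before Screening: 90 days (Table 4, footnote e; Section 9.9.10).
- ADL look-back before Screening: none is provided, so 0 days.
- Week 24, 36 and 48 visits: Days 168, 252 and 336, each ±3 days, which is 167, 251 and 335 days after Day 1.

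**Age at first dose = screening lead + look-back**
- ADL: 1 to 60 days (60 + 0 = 60 at most).
- ECG taken at Screening: 1 to 60 days.
- Historical ECG: at most 60 + 90 = 150 days.

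**Effect on the ADL change interval (60-day lead against the nominal interval from Day 1)**
- Week 24: 60/167 = 36%.
- Week 36: 60/251 = 24%.
- Week 48: 60/335 = 18%.
- With the visit window, the interval from ADL baseline to Week 48 runs from 335 + 1 - 3 = 333 days to 335 + 60 + 3 = 398 days.

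**Comparison with Part 1**
Under Table 3's footnote g (30-day look-back, Screening from Day -28) the screening ECG could be 28 + 30 = 58 days old. Taking the 90 days of Section 9.9.10 instead gives 28 + 90 = 118. Either way a Day 1 ECG follows, so the latest scheduled pre-treatment ECG is 0 days old.

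**After the change**
With both assessments made before dosing on Day 1, the maximum age falls from 60 to 0 days for ADL and from 150 to 0 days for the scheduled ECG, with no added visit.

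**What cannot be computed**
The documents give no ADL progression rate or standard deviation and no distribution of screening leads or ECG ages. The added noise cannot be put in ADL points or power, and the 150-day case has no known frequency.

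**The case against.** The strongest reply concerns the ECG. A reader might infer that the baseline for the eight later ECGs is a 150-day-old tracing. The documents do not say so. Footnote e and Section 9.9.10 let an older ECG serve for eligibility; neither calls it the analysis baseline. The protocol leaves analysis detail to the SAP (Section 14.3), and the only SAP document supplied is a short addendum on sparse sites, so the ECG baseline definition cannot be checked. What stands is narrower: no later pre-treatment ECG appears in the ECG row.

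A reader might also infer that no Day 1 tracing exists at all. That goes too far as well. The exercise test is scheduled on Day 1, and its form in Appendix 2 asks, under resting supine data, "Was resting ECG collected". But Section 9.9.26 presents Appendix 2 as an example, the form shown is for Week 48, and it does not say that the ECG is 12-lead or the one required by Section 9.9.10. It may close the gap at some sites; it cannot be assumed to close it at all of them, nor can a Day 1 ECG be assumed to cost nothing.

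A third inference would be that the treatment comparison is biased. It is not. Both baselines precede randomisation, the same window applies to both arms, and Part 2 is double-blind and allocated 1:1. Same-day vital signs, chemistry, BNP and NT-proBNP also mean that cardiac safety is not without a Day 1 reference.

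On ADL, it is fair to say that the endpoint is exploratory, that Day 1 is already full, and that items such as choking, falls and bladder function are graded by weekly or monthly frequency, so a single day is not a sharp baseline for them. These points limit the gain. They do not alter the fact that Screening is the only pre-treatment ADL value, which no SAP definition can change.

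**Conclusion.** The point holds at minor severity. For ADL it is firm: the sole pre-treatment value is 1 to 60 days old, which lengthens the change interval by up to 18% at Week 48 and up to 36% at Week 24, unevenly across patients. For ECG it is conditional: 150 days is a worst case that needs both the oldest permitted recording and the earliest permitted Screening, and it describes the scheduled ECG row, not a stated analysis baseline.

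The consequences are noise and a variable interval in an exploratory endpoint, and weaker individual-level attribution of ECG changes to before or after dosing. The conclusion assumes that Table 4 lists all scheduled safety ECGs and that the Appendix 2 tracing is not already designated as the baseline in a document not supplied.

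**What to change.** In the plan as written, and in later protocols that reuse this schedule:
- **ADL:** move the mark from Screening to Day 1, before first dose, and define that value as the ADL baseline. No eligibility criterion uses ADL, so nothing at Screening depends on it.
- **ECG:** mark an ECG on Day 1 before the exercise test, recorded as a 12-lead according to Section 9.9.10, and define it as the safety baseline. The resting tracing on the Appendix 2 form can serve if it meets that section. Footnote e stays as it is, for eligibility.

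The cost is two table cells and the baseline definitions, a few minutes for a 9-item form at a full visit, and one extra resting ECG at any site whose exercise-test tracing is not a 12-lead.

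Appendix 13 says that Part 2 was already complete when the pandemic began, so missing Day 1 data cannot be recovered. For this trial, state in the report which ECG served as baseline, and give the distribution of the age at first dose of the ECG and ADL baselines by arm.

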**Table 5: Extension Schedule of Assessments**

Study Day/Week	Screening a	Day 1 b	Week 2 (telephone)	Week 4	Week 10	Week 16	Week 24 + Every 24 Weeks	End of Study
Day Relative to First Dose in Extension	-30 to -1	1	14 (±3 days)	28 (±3 days)	70 (±3 days)	112 (±3 days)	168, 336, 504, etc. (±14 days)	Within 30 days after last dose
Informed consent	X							
Inclusion/Exclusion	X	X						
Pes cavus assessment	X							
Medical history	X							
Adverse event collection		X c	X	X	X	X	X	X
Prior and Concomitant medications	X	X	X	X	X	X	X	X
Weight and BMI	X	X d		X	X	X	X	X
Vital sign measurements	X	X d		X	X	X	X	X
Physical examination	X	X d		X	X	X	X	X
Height	X			X j				
Echocardiogram e	X							
Electrocardiogram e	X							
Clinical Chemistry	X			X	X	X	X	X
Hematology	X			X	X	X	X	X
Urinalysis and microscopy	X			X	X	X	X	X
BNP and NT-proBNP f	X			X	X	X	X	X
Hepatitis B and C and HIV 	X							
Pregnancy test WOCBP h	X	X		X	X	X	X	X
Dispense study drug		X		X			X	
Study drug return and pill count				X			X	X
Neurologic FARS		X					X	X
Activities of Daily Living		X					X	X
Patient Global Impression of Change							X	
Clinical Global Impression of Change							X	
25-foot Timed Walk Test		X					X	X
9-Hole Peg Test		X					X	X

Abbreviations: BMI=body mass index; BNP= B-type natriuretic peptide; FARS=Friedreich's ataxia rating scale; HIV=human immunodeficiency virus; NT-proBNP= N-terminal prohormone of B-type natriuretic peptide; WOCBP=women of childbearing potential.

a The screening visit is only required for Part 1 patients. Assessments collected at Part 2 - Week 48 or Part 2 - Week 52 should be used to assess eligibility for Part 2 patients.

b On Day 1, all required procedures should be performed and eligibility confirmed before study drug is dispensed in the extension.

c Adverse event assessments on Day 1 should be performed following study drug administration.

d For patients enrolled in Part 2 of the study, visit procedures required at Week 52 and also Extension Day 1 should only be performed once since Part 2 Week 52 and Extension Day 1 should occur on the same day.

e For patients with echocardiograms and electrocardiograms collected within 90 days prior to the Screening Visit, the most recent echocardiogram and electrocardiogram can be used to assess patient eligibility.

f Patients must be allowed to rest for a minimum period of 1 hour following maximal exercise test before this blood sample is collected (at the same time as all central lab blood draws). This sample should be taken with the patient in the same position (e.g., sitting or semi-recumbent) at all appropriate visits.

- g Blood samples should be collected for hepatitis B and C and HIV antibodies only in patients lacking evidence of a negative titer in the past year.
- h A serum pregnancy test will be performed at any point in time if a pregnancy is suspected. All other pregnancy assessments will be urine pregnancy tests. Additional pregnancy assessments will be performed more frequently if required by local law or requested by local health authorities or IRBs/ECs.
- i Patients and investigators must complete the patient global impression of change and clinical global impression of change following completion of the neurological FARS exam.
- j Height will be performed at Week 4 for Part 2 patients enrolled in the Extension.

## **8. SELECTION AND WITHDRAWAL OF PATIENTS**

### **8.1. Patient Inclusion Criteria (Part 1 and Part 2)**

Patients must:

1. Have genetically confirmed Friedreich's ataxia
2. Have an mFARS score  $\geq 20$  and  $\leq 80$ . The average of the two mFARS values collected at Screening and Day 1 visits must fall within the allowable range, and they must be within 4.5 points of each other
3. Be male or female and  $\geq 16$  years of age and  $\leq 40$  years of age
4. Have no changes to their exercise regimen within 30 days prior to Study Day 1 and be willing to remain on the same exercise regimen during the study period
5. Have the ability to complete maximal exercise testing
6. Have adequate kidney function defined as an estimated glomerular filtration rate (eGFR)  $\geq 60$  mL/min/1.73 m^2 using the Modification of Diet in Renal Disease (MDRD) 4-variable formula
7. Have a left ventricular ejection fraction  $\geq 40\%$  (based on echocardiogram performed at Screening Visit or within 90 days prior to Screening Visit)
8. Be able to swallow capsules
9. Be willing and able to cooperate with all aspects of the protocol
10. Be willing to practice medically acceptable methods of birth control (Section 9.7.2)
11. Provide written informed consent for study participation, approved by the appropriate Institutional Review Board (IRB)

### **8.2. Patient Exclusion Criteria (Part 1 and Part 2)**

Patients must not:

1. Have uncontrolled diabetes (HbA1c  $> 11.0\%$ )
2. Have a BNP level  $> 200$  pg/mL
3. Have a history of clinically significant left-sided heart disease and/or clinically significant cardiac disease, with the exception of mild to moderate cardiomyopathy associated with Friedreich's ataxia, including but not limited to any of the following:
  - a. Clinically significant congenital or acquired valvular disease
  - b. Pericardial constriction (based on echocardiogram performed at Screening Visit or within 90 days prior to Screening Visit)
  - c. Restrictive or congestive cardiomyopathy (based on echocardiogram performed at Screening Visit or within 90 days prior to Screening Visit)

- d. Symptomatic coronary disease (prior myocardial infarction, percutaneous coronary intervention, coronary artery bypass graft surgery, or angina)
  - e. History of hospitalization for heart failure in the last five years
  - f. Cardiac insufficiency, defined as New York Heart Association Class > 2
  - g. History of atrial fibrillation
  - h. History of unstable arrhythmias
4. Have known active fungal, bacterial, and/or viral infection, including human immunodeficiency virus (HIV) or hepatitis virus (B or C)
  5. Have known or suspected active drug or alcohol abuse, as per investigator judgment
  6. Have clinically significant abnormalities of clinical hematology or biochemistry, including but not limited to elevations greater than 1.5 times the upper limit of normal (ULN) of AST or ALT. Levels above this threshold are allowable if attributable to muscle injury
  7. Have any abnormal laboratory test value or clinically significant pre-existing medical condition that, in the opinion of the investigator, would put the patient at risk by study enrollment
  8. Have taken any of the following drugs within 7 days prior to Study Day 1 or plan to take any of these drugs during the time of study participation:
    - a. Sensitive substrates for cytochrome P450 2C8 or 3A4 (e.g., repaglinide, midazolam, sildenafil)
    - b. Moderate or strong inhibitors or inducers of cytochrome P450 3A4 (e.g., carbamazepine, phenytoin, ciprofloxacin, grapefruit juice)
    - c. Substrates for p-glycoprotein transporter (e.g., ambrisentan, digoxin)
  9. Have a history of clinically significant liver disease (e.g., fibrosis, cirrhosis, hepatitis), or has, at screening, clinically relevant deviations in laboratory tests including any one of the following:
    - a. ALT and/or AST > 1.5-fold ULN,
    - b. bilirubin > 1.2-fold ULN,
    - c. ALP > 2-fold ULN,
    - d. albumin < lower limit of normal (LLN)
  10. Have participated in any other interventional clinical study within 30 days prior to Study Day 1
  11. Have a cognitive impairment that may preclude ability to comply with study procedures
  12. Be unable to comply with the requirements of the study protocol or be unsuitable for the study for any reason, in the opinion of the investigator

13. Have used antioxidant supplements, including but not limited to idebenone, coenzyme Q10, nicotinamide, and vitamin E above the recommended daily allowance, within 14 days prior to Study Day 1 or plan to take any of these supplements during the time of study participation
14. Have previously documented mitochondrial respiratory chain disease
15. Have a history of thromboembolic events within the past 5 years
16. Have taken anticoagulant therapy within 30 days prior to Study Day 1
17. Have scheduled surgical treatment for scoliosis or foot deformity during the study
18. Have had significant current suicidal ideation within 1 month prior to Screening Visit as per investigator judgment or any history of suicide attempts
19. Be pregnant or breastfeeding
20. Prior participation in a trial with RTA 408

